9.6 Analysis Cohorts

Different groups of subjects, or Analysis Cohorts, will be identified depending on the type and extent of analysis being performed.

Only subjects from study centers located within the United States and study centers located O.U.S. that have been enrolled under this version of the protocol (2.6) will be included in the analyses and data presentations defined in this protocol.

Screening Cohort

All subjects who are consented and screened for the study will be included in the Screening Cohort. Subjects excluded during the procedure from receiving Jada treatment for non-device related reasons are included in this Cohort. Only an accounting of the numbers of subjects screened in the study, plus the reasons given for subjects not enrolled in the study will be performed on this Cohort.

Safety/ITT (Intent to Treat) Cohort

All subjects in whom treatment was attempted with Jada (device inserted and vacuum turned on) are included in the Safety/ITT Cohort.

Per-Protocol Cohort

The Per-Protocol Cohort is defined as the group of subjects who are treated and complete treatment with the Jada System per the device's Instructions for Use, and who complete their 6-week visit without any major protocol deviations.

Cohort for Primary and Secondary Effectiveness Endpoints

Analyses of all primary and secondary effectiveness endpoints will be repeated both for the Safety/ITT Cohort and for the Per-Protocol Cohort. Study Success will be based on the Safety/ITT Cohort.

Cohort for Safety Endpoints

Analyses for all safety related endpoints will be performed using the Safety/ITT Cohort.

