3.5 First in Human Study Feasibility Study

A First-in-Human (FIH) feasibility investigational study with Ethics Committee oversight was conducted at two clinical sites in Indonesia. The purpose of the study was to demonstrate the placement, function, and operation of the Jada System to meet its intended use to reduce or control PPH.

Ten women were enrolled between July 2014 and February 2015. None of the subjects presented with a retained placenta, uterine lacerations, uterine scarring, or for any conditions other than atonic post-partum hemorrhage. The Jada was successfully placed and activated in all ten subjects. A vacuum force of 70 mmHg - 90 mmHg was used for treatment. The average time from placement of the Jada to removal was 152.0 ± 111.7 minutes (range 60-390 minutes).

Bleeding was controlled within two minutes for all ten subjects. Evaluation of the primary clinical data safety endpoints determined that: 1) no safety issues were observed relative to the placement, insertion, or removal of the Jada, 2) there were no complications related to delayed arrest of blood loss, 3) there was no damage to the uterus, cervix, or vagina, and 4) no uterine inversion or folding events were observed during the Jada procedure.

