5.4.4 Subject Withdrawal and Termination

Subjects will be advised that they may voluntarily withdraw from the study at any time and will be instructed to notify the Investigator immediately if they choose to withdraw. A subject may choose to withdraw for any reason and is not obligated to reveal reason(s) for withdrawal. Any data contributed up to the point of withdrawal will be included in the analyses. In addition, any adverse events that are ongoing at the time of the subject's withdrawal will be marked as such on the Adverse Event case report form. Subjects will be followed until the adverse event is resolved or is not expected to change.

Subjects may also be involuntarily terminated from the study by the Investigator if the Investigator believes it is in the best interest of the subject. This may occur if the investigator believes more aggressive treatment is necessary prior to the use of Jada. This may also occur if the Investigator decides to abort the treatment with Jada after it is inserted. If a Jada is inserted in the subject but treatment is aborted thereafter, the subject will be followed for six weeks.

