5.6 Justification for Study

A feasibility clinical study of the Jada System has been completed with encouraging results. See the Clinical Evaluation Report (G150265, Attachment H, pages 337-382). In this feasibility study, Jada was used in a limited population of women who had failed first line conservative therapy. This study excluded subjects delivering by Cesarean section and subjects with other major identifiable causes of PPH other than atony. This conservative subject selection process was deliberately chosen to reduce the variance in the treated population in order to clearly demonstrate the device's mechanism of action and allow safety to be elucidated. In all ten subjects, PPH ceased within two minutes. The Jada System was left in place for up to 6.5 hours. None of the subjects experienced a device-related adverse event.

Subsequent to this Feasibility Study, clinical use of vacuum via uterine cannula (different device than the Jada) to create uterine tamponade was reported by Ram et al in 2014.²⁵ Sixteen women who had vaginal deliveries and four women who underwent Cesarean sections were included in the study. All women received 10 units of oxytocin at the appearance of the baby's anterior shoulder, 5 units of intravenous oxytocin after the delivery of the placenta, and then uterine massage. Carboprost 125 mcg was also given when the bleeding did not stop. All 20 women were then administered the uterine vacuum retraction system via rigid cannula and vacuum forces of 650 mmHg for 10 minutes at a time. Complete cessation of bleeding which was associated with contraction and firm retraction of the uterus

PEARLE Study

was observed in all women within 4 minutes of initiation of the procedure. The clinical outcomes for the vaginal deliveries and Cesarean sections were comparable. No adverse events were reported.

These early studies demonstrated the safety and initial effectiveness of the use of a vacuum to create uterine tamponade and treat postpartum hemorrhage. This Pivotal Study is designed to gather more data demonstrating the safety and effectiveness of the Jada System in a larger patient population. Meta-analysis methodology was used to establish target endpoints which will demonstrate the safety and effectiveness of the Jada System; as such, the resulting design is a literature-controlled study design.

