9.3 Primary Effectiveness Endpoint – Treatment Success

Control of postpartum hemorrhage, defined as the avoidance of non-surgical, second line or surgical intervention to control uterine hemorrhage after the use of the Jada System per the Instructions for Use.

Non-surgical, second line procedures include uterine balloon therapy, uterine packing, or uterine artery embolization. Surgical intervention includes procedures such as uterine arterial ligation, uterine compression sutures or hysterectomy.

Note: Continuation of the administration of uterotonics concomitant with and post Jada use is standard of care as long as such use does not exceed the maximum dose of the drug and does not constitute failure of the primary effectiveness endpoint.

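### Section 9.6 leaves an enrolled woman in whom insertion was attempted but vacuum was never applied out of every effectiveness and safety analysis

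*Combined protocol and SAP*

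**What the plan says.** Section 9.6 sets the entry rule for the Safety/ITT Cohort: "All subjects in whom treatment was attempted with Jada (device inserted and vacuum turned on) are included in the Safety/ITT Cohort". The parenthesis has two conditions and both must be met. The same section bases Study Success on this cohort and adds: "Analyses for all safety related endpoints will be performed using the Safety/ITT Cohort".

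The other cohorts do not fill the gap. Per-Protocol is narrower, since it needs completed treatment per the IFU and a completed six-week visit. The Screening Cohort takes in everyone consented and screened, but is used only to count subjects and list reasons for non-enrollment. On exclusion during the procedure it says: "Subjects excluded during the procedure from receiving Jada treatment for non-device related reasons are included in this Cohort". Device-related reasons are not mentioned.

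Sections 5.5 and 6.4 define enrollment as consent plus eligibility, before any device use. Section 6.5 places the loop and fills the seal before vacuum is applied. Section 5.4.4 addresses aborted treatment without a vacuum condition: "If a Jada is inserted in the subject but treatment is aborted thereafter, the subject will be followed for six weeks".

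**The concern.** Between enrollment and vacuum-on lies the insertion step, where a device can fail to seat, malfunction or cause injury. Section 3.6.1 names perforation or injury on insertion as a risk. A woman in whom vacuum is never applied falls outside both primary endpoint analyses, even if she is injured by the attempt or goes on to balloon, packing, embolization or surgery. If her treatment is aborted after insertion, 5.4.4 has her followed for six weeks, yet no table receives her data.

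The missing-equals-failure rule in 9.12 works within the analysis cohort and does not add anyone to it. An exclusion made after enrollment, for a reason that may be related to outcome, is then built into a single-arm rate compared with a fixed bar.

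The adverse event start point adds to the ambiguity. It is enrollment in 7.3 but the beginning of device use in 6.6 and 7.2, and no text says whether a failed insertion is device use.

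**Working it through.** **Inputs from the documents.** Bar 73.4% on the lower limit of the two-sided 95% mid-p interval (4.3, 9.4); 96 evaluable and 107 enrolled (5.4.1); expected success 82% (5.4.1). The enrollment figure reproduces: 96/(1 − 0.10) = 106.7, rounded up to 107. The plan gives no rate of pre-vacuum failure.

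**What is known about that rate.** The feasibility study (3.5) reports: "The Jada was successfully placed and activated in all ten subjects". That is 0/10, with exact upper 95% limit 1 − 0.025^(1/10) = 0.308. Seeing 0/10 has probability 0.99^10 = 0.904 at a true 1% and 0.95^10 = 0.599 at 5%. Section 5.6 adds: "This study excluded subjects delivering by Cesarean section". The pivotal trial includes Cesarean deliveries and trans-abdominal placement.

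**One case at the bar.** The mid-p lower limit p_L for x successes in n solves P(X > x | n, p_L) + ½·P(X = x | n, p_L) = 0.025.

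- 79/96: 0.7369, pass (79 is the smallest passing count at n = 96). 79/97: 0.7278, fail.
- 87/106: 0.7390, pass. 87/107: 0.7308, fail.

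Further from the bar it takes more added failures to reverse a pass at n = 96: 2 at 80 successes, 3 at 81, 5 at 82, 6 at 83. The chance of landing exactly on 79/96 at a true 82% is 0.106.

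**Chance of passing against an all-attempt null.** Assume 107 attempts, a share q never reaching vacuum, and a share s of those needing second-line or surgical treatment. Fix the success rate over all attempts at 0.734. The rate among vacuum-on women is then p = (0.734 − q(1 − s))/(1 − q). For example, q = 0.05 and s = 1 give 0.734/0.95 = 0.773. The number excluded is K ~ Bin(107, q). The pass probability averages P(X ≥ r | n = 107 − K, p) over K, where r is the smallest passing count at that n (88 at 107, 87 at 106, 86 at 105, 85 at 104 and 103, 84 at 102).

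| q (assumed) | s = 1 | s = 0.5 | s = 0.266 | s = 0 |
|---|---|---|---|---|
| 1% | 3.6% | 2.8% | 2.5% | 2.1% |
| 2% | 5.4% | 3.3% | 2.6% | 2.0% |
| 3% | 7.6% | 3.7% | 2.6% | 1.7% |
| 5% | 13.9% | 4.6% | 2.5% | 1.2% |

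With no exclusions it is 2.2%. The neutral share is s = 1 − 0.734 = 0.266, where p stays at 0.734; the small departures from 2.2% in that column come from the discreteness of the rule.

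**The case against.** The strongest reply is that 5.4.1 states the hypothesis for women treated with Jada, and the benchmark is hemostasis following balloon treatment. On that reading 9.6 matches the plan's own parameter. A reader might take the table as inflation of the plan's type I error. The documents do not support that: the table uses a different null, the all-attempt rate, and assumed values of q and s. This part of the objection stands. So does its companion: the literature denominator is in an attachment that is not available here. If the literature counted only placed balloons, widening the Jada side alone would tilt the comparison against Jada.

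The endpoint wording might also suggest that a woman without vacuum can never be a success, since it refers to "surgical intervention to control uterine hemorrhage after the use of the Jada System per the Instructions for Use". Those words can equally define who is assessed. A blanket rule would also fail women stopped for non-device reasons, whom 9.6 deliberately places in the Screening Cohort.

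A reader might infer that these women vanish from the trial, or that any injury before vacuum is lost. Neither follows. Adverse events are collected and adjudicated (7.3), serious ones are reported (7.4), and device failures and use errors are documented (7.5). If vacuum is later turned on, the woman is in Safety/ITT and her insertion injury counts. Aborts after vacuum-on also stay in.

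Nor do other sentences clearly override 9.6. Section 5.4.4 says "Any data contributed up to the point of withdrawal will be included in the analyses", but of voluntary withdrawal. Section 9.11 concerns loss to follow-up and withdrawal, and 9.1 is a general introduction. None names a cohort.

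Finally, such cases may be rare, and any threshold can be crossed by one subject. Both are true. But 0/10 cannot establish rarity, and the safety gap does not depend on the bar.

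**Conclusion.** The gap is real on the text and should be fixed. It concerns enrolled women in whom insertion was attempted and vacuum was never applied; they are missing from analysis, not from data capture.

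The safety half is firm. Insertion is a named hazard, the primary safety endpoint is device-related adverse events, and the cohort rule can drop exactly such an event.

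The effectiveness half is a choice of estimand. Whether the vacuum-on rate or the all-attempt rate is the right comparison with 73.4% depends on how the literature rate was counted.

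The size is nil without such cases. At the bar a single excluded failure decides the trial. Against an all-attempt null of 73.4%, with 107 attempts and 1% to 5% excluded, the chance of passing is 3.6% to 13.9% if all excluded women need further treatment. It is about 2.5% if 27% do and 2.1% to 1.2% if none do, so the direction is not fixed. Confidence is high in the reading of 9.6 and low in any particular magnitude.

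**What to change.** 1. **Safety cohort (9.6).** Define it as every enrolled subject in whom insertion of Jada was attempted. Use one adverse event start point that covers attempted insertion, reconciling 7.3 with 6.6 and 7.2.
2. **Accounting (9.6).** Assign device-related pre-vacuum failures to a named cohort, and report all pre-vacuum failures with reasons.
3. **Effectiveness (9.3, 9.6).** Prespecify an analysis that adds attempted insertions not stopped for non-device reasons to the vacuum-on set. Score Treatment Success = No for second-line or surgical intervention or a missing outcome, with no blanket rule for women in whom vacuum was never applied. Make this the primary set if the literature rate was counted per attempt. Otherwise report it as a sensitivity analysis beside the vacuum-on result. Settle this from the Clinical Evaluation Report before outcomes are seen.
4. **Time to control.** Keep the vacuum-on set, since that endpoint starts when the vacuum is turned on.

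**Cost.** Mostly wording. The case report forms are not in the documents, so small additions to data capture may be needed. The six-week sentence in 5.4.4 covers only women in whom the device was inserted, so follow-up data for failed insertions may need a line too.

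If the wider set becomes primary and such cases occur, the chance of passing falls. Take the least favorable case: 107 attempts, vacuum-on success 82%, and every added woman a failure. With 1%, 2% or 5% never reaching vacuum (assumed), the counted rate is 0.82 × (1 − q) = 81.2%, 80.4% or 77.9%. The chance of passing is then 45%, 36% or 17%, against 55%, 56% or 54% under the current rule. With no such cases it is 53% under both; the difference between that and the 0.806 in 5.4.1 is a separate point. As a sensitivity analysis, the change leaves the Study Success rule untouched.

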6.5 Intervention

The Investigator will use Jada in conjunction with the device's Instructions for Use that is included with every device. Following the steps of the IFU and according to their training, the Investigator will place the Jada intrauterine loop into the uterus. For vaginal deliveries, the device will be placed transvaginally; for Cesarean deliveries, the device will be placed trans-abdominally or transvaginally (if the hysterotomy was closed first). The vacuum seal will be filled with 60 ml sterile IV fluid. Vacuum forces will be applied to suction residual blood and debris. Once the residual blood is removed, the pressure gradient from the vacuum creates a uniform mechanical stimulus on the uterus, causing it to collapse into and onto itself. At that time, tamponade occurs and hemorrhage is expected to be controlled. Vacuum forces will be maintained for at least one hour (from the time hemorrhage is controlled) until the subject is stable or until the Investigator determines that hemorrhage was not

PEARLE Study CIP-01 v2.6 controlled and further intervention is needed. If any further intervention is required to treat the PPH, it will be reported on the Procedure case report form, capturing details on the intervention.

Once the Investigator detaches the tubing from the device or "zero's" the vacuum source and the seal is emptied of the fluid, the device should remain in place and taped to the patient's inner thigh for at least 30 minutes, provided the subject is stable and there is no medically valid reason to remove the device. The 30-minute minimum observation period allows for the Investigator to re-initiate treatment should the uterus return to an atonic state with abnormal bleeding.

If the subject remains stable and the PPH does not return for 30 minutes, then the device can be removed and decommissioned (cut up) prior to final disposal. Device pieces should be discarded in accordance with hospital biohazardous waste policies. If there was a device malfunction, the Investigator or designee should wrap the device in a biohazardous disposal bag and contact Alydia Health for further instructions to return the device for evaluation.

Other standard of care medical evaluation and care must be ongoing during the use of the Jada System. If it is determined that blood products must be administered, then the Investigator should follow the local protocol to do so.

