6.8 Summary Table of Clinical Assessments

The schedule of clinical assessment is outlined in Table 2.

Table 2: Clinical Assessment Schedule

Procedure/Assessment	Baseline	Jada Procedure through discharge	6-Week Follow-up 42 days ± 14 days
Screening for inclusion / exclusion	√		
Informed Consent and HIPAA authorization	√		
Enrollment		\checkmark	

Demographics, history and delivery data collection	√		
General exam	√ (after delivery but prior to PPH dx)	√ (after Jada use and prior to discharge)	V
Vital Signs (at admission)	\checkmark		
CBC / Coag Panel	√* (at admission)	* (after Jada use and prior to discharge)	
Jada procedure and endpoint assessment		V	
Investigator assessment of device usability		V	
Adverse Event assessment		\checkmark	\checkmark
Assessment of medications that may affect bleeding	√	V	
Study exit			V

 $[\]sqrt{*}$ If an Investigator deems it medically important to conduct the CBC or coagulation panel, the results of these should be recorded in the Baseline and Post-Procedure Through Discharge case report forms.

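### The Per-Protocol effectiveness analysis requires the 6-week visit, so it can drop women already recorded as failures; Study Success, decided on Safety/ITT, is unaffected

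*Combined protocol and SAP*

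**What the plan says.** Section 9.6 defines the Per-Protocol cohort as "the group of subjects who are treated and complete treatment with the Jada System" in line with the device's "Instructions for Use, and who complete their 6-week visit without any major protocol deviations". It then states: "Analyses of all primary and secondary effectiveness endpoints will be repeated both for the Safety/ITT Cohort and for the Per-Protocol Cohort". The decision rule is kept apart: "Study Success will be based on the Safety/ITT Cohort". Safety analyses also use Safety/ITT, which a woman enters once the device is inserted and the vacuum is turned on, with no completion or follow-up condition.

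The other relevant places are these:

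- Section 6.8, Table 2: the row "Jada procedure and endpoint assessment" carries one mark, read as the column running from procedure to discharge. The adverse event row carries two marks, the second at 6 weeks.
- Section 6.7: the 6-week visit consists of a physical examination with limited pelvic examination and an adverse event assessment. After three documented failed attempts, adverse events are collected by phone instead.
- Section 8.3: sites must try at least three times to reach a woman, once by registered letter, and hold details of two contact persons.
- Section 9.3: Treatment Success is the avoidance of second-line or surgical intervention after device use. No closing time is given.
- Section 9.12: a missing Treatment Success outcome counts as failure.

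**The concern.** The cohort for an effectiveness analysis is selected on an event that comes weeks after treatment and, on the face of Table 2, after effectiveness has been assessed. A woman can have a balloon, embolization or hysterectomy recorded on the Procedure case report form, miss the later visit, and leave the Per-Protocol analysis. Her outcome is known and nothing at the visit could reverse it.

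What is at stake is limited. The Per-Protocol rate enters no success rule. It is nevertheless a planned result shown beside the Safety/ITT rate, and in a single-arm study a reader will take agreement between the two as a check on robustness. A cohort that can lose known failures, or known successes, through later attendance is a poor check.

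**Working it through.** The plan gives no Per-Protocol figure to reproduce, so the check is mainly a reading of the text, followed by an illustration of size.

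**Step 1. When is effectiveness assessed?** Table 2 marks endpoint assessment once, before discharge, and does not mark it at 6 weeks. Section 6.7 lists no effectiveness item for the 6-week visit. The two agree with each other, and neither explains why an effectiveness cohort should depend on that visit.

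**Step 2. Whose outcome is certainly known without the visit?**

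- Intervention already recorded: the woman is a failure under Section 9.3 whatever the closing time.
- No intervention recorded by discharge: her outcome is complete only if Table 2 sets the closing time, because Section 9.3 sets none.

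The visit condition therefore discards known outcomes for the first group on any reading, and for the second group only on the Table 2 reading.

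**Step 3. How many women?** The documents do not say. Sections 6.7 and 8.3 should keep the number down, but the plan does not state whether a phone contact counts as completing the visit.

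**Step 4. Size, with assumed counts.** Section 5.4.1 gives 96 evaluable women and an expected rate of 82%. Since 96 × 0.82 = 78.7, take 79/96 = 82.3% as the Safety/ITT result, with outcomes known at discharge. If s successes and f failures miss the visit and no one else is excluded, the Per-Protocol rate is (79 − s)/(96 − s − f).

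| Missed (assumed) | s | f | Per-Protocol rate |
|---|---|---|---|
| 3 | 3 | 0 | 76/93 = 81.7% |
| 3 | 2 | 1 | 77/93 = 82.8% |
| 3 | 1 | 2 | 78/93 = 83.9% |
| 3 | 0 | 3 | 79/93 = 84.9% |

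The first and last rows are extremes. The rate falls if only successes are lost and rises if failures are over-represented among the missed visits.

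**Step 5. The same arithmetic with recorded failures kept in.** The rate becomes (79 − s)/(96 − s). For s from 3 to 0 this runs from 76/93 = 81.7% to 79/96 = 82.3%. Keeping known failures removes the upward part of the range.

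**Step 6. The words on completing treatment.** Section 6.5 says "Vacuum forces will be maintained for at least one hour (from the time hemorrhage is controlled"), a point that an uncontrolled bleed does not reach. Section 5.4.4 recognises termination by the Investigator: "This may also occur if the Investigator decides to abort the treatment with Jada after it is inserted". Read together, these could place a non-responder outside the cohort. But Section 6.5 continues "until the subject is stable or until the Investigator determines that hemorrhage was not" controlled and further intervention is needed. That makes non-control a planned end of vacuum, so she has completed treatment and stays in as a failure. The text supports this second reading better without closing off the first.

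**The case against.** The strongest reply is that nothing depends on this cohort. Study Success and safety rest on Safety/ITT, missing primary outcomes count as failures, and per-protocol sets commonly require follow-up as planned. This stands, and it limits the point to a supportive analysis.

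A second reply is that, with no closing time in Section 9.3, effectiveness may be meant to run to 6 weeks. The adverse event assessment at that visit could reveal a late intervention, so a success might not be final at discharge. This also stands for women without a recorded intervention. It does not justify dropping a woman whose intervention is already recorded. It does mean that removing the visit condition alone is not enough: if ascertainment runs to 6 weeks, women with incomplete outcomes would enter the cohort, and Section 9.12 might count them as failures. The window has to be settled in the same edit.

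A reader might go further and infer that the Per-Protocol rate is biased upward because completing treatment excludes failures. The documents do not establish that. It needs the less favoured reading of Section 6.5, Section 5.4.4 does not say that non-response is an abort, and the Instructions for Use, which the cohort definition relies on, are not among the documents. Section 9.3 also counts intervention after use according to those Instructions, so failure after compliant use is foreseen.

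**Conclusion.** The point holds as a minor one. Followed as written, Section 9.6 removes women from the supportive effectiveness analysis because of a later visit that has no stated effectiveness content, and this includes women who are known failures. The direction of the net effect is unknown. With three missed visits, from 82.3%, the rate would lie between 81.7% and 84.9%. That number of visits is an assumption, the ends are extremes, and the placement of the endpoint assessment rests on the single mark in Table 2.

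A reader might infer that the trial's conclusion, error rate or power is affected, or that a favourable Per-Protocol bound could rescue a failed study. Neither follows: the plan attaches no criterion to the Per-Protocol result. Nor can one say that every woman who misses the visit already has a complete outcome. That is certain only for recorded failures.

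**What to change.** 1. In Section 9.6, remove the 6-week visit as a condition for the Per-Protocol effectiveness analysis.
2. In Section 9.3, state that Treatment Success is assessed through discharge, consistent with Table 2, and carry the same wording into Sections 1.0 and 4.2.1. If the sponsor intends ascertainment to 6 weeks, say so, and at minimum keep every woman with a recorded second-line or surgical intervention in the cohort as a failure. In that case also state whether a phone contact counts as the visit.
3. In Section 9.6, state that, for this analysis, a woman treated per the Instructions for Use and then escalated because bleeding was not controlled has completed treatment and stays in as a failure.

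These are counting rules for the analysis and change nothing in device use, follow-up or sample size. The cost is revised wording, mainly in Section 9, which is part of the protocol. Section 9.6 limits the analyses to women enrolled under version 2.6, so that sentence must be kept consistent with any new version number. The supportive rate may look less favourable. The change should be made before outcome data are seen.
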